12 The Pease feasibility assessment included sample size calculations for a wide range of health related 13 outcomes (ATSDR 2017a). Sample size calculations selected a type 1 (" α error") of .05 and type 2 error 14 ("β error") of .20. The tables present sample sizes per stratum for specific outcomes for children (Table 15 1) and for adults (Table 2). To determine effect sizes that are reasonable to detect, we selected epidemiological studies using NHANES data. For those outcomes not included in NHANES studies, the C8 16 17 studies were used. The C8 results were considered more representative of U.S. populations (e.g., in 18 background disease rates and prevalence of non-PFAS risk factors) than studies conducted in other 19 countries, although the PFOS, and especially the PFOA, serum levels in the C8 studies were higher than 20 might occur at other sites. For outcomes not evaluated by NHANES or C8 studies, it was necessary to use 21 studies conducted in other countries. The total sample sizes for children and adults should allow for the 22 categorization of PFAS serum levels (or cumulative PFAS serum levels) into e.g. quartiles of exposure: 23 reference level, low, medium and high.

Attachment 3 includes additional information and assumptions pertinent to selected health outcomes to
 be studied.

26 3.3.1 Children

For children, **Table 1** (and **Attachment 3a**) provide the sample size calculations for several health outcomes of interest assuming a type 1 (" α error") of .05 and type 2 error (" β error) of .20. It was considered important that a study have a total sample size so that exposures could be categorized into tertiles (i.e., reference, medium, and high) or preferably into quartiles (i.e., reference, low, medium and
high). Per stratum estimates of needed sample size have been calculated based on different prevalence
of outcomes and detected odds ratios or mean difference.

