4 The proposed sample size of 2,000 children (equally of both sexes) is large enough to effectively evaluate 5 many of the health outcomes identified in the Pease Feasibility Assessment literature review and the 6 recent systematic review (Rapazzo 2017) as potentially associated with PFAS in children. The health 7 outcomes and biomarkers studied would include mean difference in total cholesterol (ranging from 156 8 to 637 per stratum), uric acid levels (556 per stratum), estimated glomerular filtration rate (eGFR; 275 per 9 stratum), testosterone (about 400 per stratum) and insulin growth factor-1 (IGF-1; 146 per stratum). 10 Based on our estimations, we would also be able to detect differences in risk for obesity and atopic 11 dermatitis. A sample size of 2,000 children would be larger than many of the PFAS studies that evaluated 12 neurobehavioral outcomes such as IQ and ADHD (Wang 2015, Stein 2013, 2014, Fei 2011, Hoffman 2010, 13 Strom 2014).

An NHANES study of estimated glomerular filtration rate observed statistically significant findings with a total sample size of just under 2,000 children (Kataria 2015). For thyroid function, estradiol, delayed puberty, and asthma, a total sample sizes of 2,000 children may be sufficient, although larger sample sizes would be optimal (Lopez-Espinosa 2011, 2012; Stein 2016).

In summary, a total sample size of ≥2,000 would be sufficient to evaluate a wide range of biomarkers and
 outcomes including lipids (and hypercholesterolemia), uric acid (and hyperuricemia), estimated
 glomerular filtration rate, testosterone, IGF-1, neurobehavioral measures (executive function, attention,
 IQ) and ADHD, rhinitis, and obesity.

Health-related Endpoint	Relevant Study	Observed Effect Size	Assumptions	Sample Size/Stratum α error = .05 β error = .20
Total Cholesterol	Frisbee 2010, C8 Study	PFOS: 5 th vs 1 st quintile Age: <12 vrs 12-18	Mean PFOS serum levels were about 20	+4.6: 637/stratum
(mg/dL)	1,971 boys <12 yrs 2,773 boys 12-18 yrs 1,886 girls <12 yrs 2,520 girls 12-18 yrs	Boys: +6.2 +9.3 Girls: +4.6 +9.4	μg/L. SD for total cholesterol=29.3 mg/dL	+9.3: 156/stratum
High cholesterol		OR = 1.6	Prevalence=34.2%	300/stratum

22 **Table 1.** Sample size estimations for selected health-related endpoints in Child Study (ages 4-17 years)

Thyroid	Lopez-Espinosa 2012,	PFOS, 4 th vs 1 quartile:	Mean PFOS serum	1,080/stratum

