function	C8 1.078 1-5 yrs	2.3% change (mean difference = 0.17 µg/dI)	levels were about 20 $\mu g/L$ SD for TT ₄ as	
114	3,132 6-10 yrs		estimated at 1.4.	
	6,447 >10 - 17 yrs		Percent change in	
			TT ₄ was converted to	
			mean difference	
			assuming the	
			median TT_4 was ref.	
Thyroid			Provalence-0.6%	>16 000/stratum
disease		(PFOS: OR < 1.0)	(used PEOA results)	210,000/stratum
Uric Acid	Kataria 2015,	PFOS: 4 th vs 1 st guartile =	Mean PFOS serum	556/stratum
	NHANES	+0.19 mg/dL	level = 12.8 μg/L. SD	,
	1,960; 12-18 yrs		= 1.19.	
Hyperuricemia	Geiger 2013,	PFOS: 4 th vs 1 st quartile,	Mean PFOS serum	400/stratum
	NHANES	OR=1.65	level =16.6.	
	1,772; 12-18 years		Prevalence=16%	
eGFR	Kataria 2015	PFOA mean serum level	Standard	275/stratum
	1,960; 12-18 yrs	=3.5 μg/L. mean	deviation=27.6	
		difference= -6.6		
Testosterone	Lopez-Espinosa 2016,	PFOS (IQR):	Percent change was	Boys: 404/stratum
	C8	-5.8% boys (diff=1.9)	converted to mean	Girls: 368/stratum
	1,169 boys; 6-9 yrs	-6.6% girls (diff=2.45)	difference assuming	
	1,123 girl; 6-9 yrs		median testosterone	
			level was ref. level.	
			SD estimated at	
			9 63 for hovs	
IGF-1 (Insulin-	Lopez-Espinosa 2016.	PFHxS (IQR):	Percent change was	146/stratum
like growth	C8	Boys: -2.5% (diff=17.3)	converted to mean	,
factor – 1)		Girls: -2.1%	difference assuming	
			median IGF-1 in boys	
			as ref. level. SD	
			estimated as 52.6	
Delayed	Lopez-Espinosa 2011.	PFOS: mean serum level	OR for delayed	to calculate sample size,
Puberty	3 072 hove 8-18 vrs	was about 19 µg/L.	puberty and the	but sample sizes in this
	2.903 girls, 8-18 yrs		delayed puberty had	study were enough for sufficient precision
	-,000 8		narrow Cls	
ADHD	Stein 2011, C8	PFHxS mean serum level		
	10,546; aged 5-18	was 5.2 µg/L. 4 th vs 1 st		
	yrs.	quartile,	Prevalence:	764/24224
		0K=1.5	AUHU UX: 12.4%	764/stratum
Asthma	Stein 2016, NHANES	PFOA mean serum level =	Prevalence = 11%	2,400/stratum
	640; 12-19 yrs	3.6 μg/L.		
		OR=1.2		
Atopic	Wang 2011 (Taiwan)	PFOS mean serum	Prevalence=10.7%	220/stratum
dermatitis	244; infants, 2 yrs	level=5.5 μg/L., 4''' quartile OR=2 19		
Obesity	Karlsen 2017	PFOA mean serum	Prevalence=17%	250/stratum
	(Faroes)	level=2.22 μg/L. OR=1.88		

1 Note: Observed effect sizes focused on the results for serum levels of PFOS and/or PFHxS.

¹ eGFR –estimated glomerular filtration rate, TT4 – total thyroxine; IGF-1 – insulin-like growth factor 1; ADHD – attention-deficit
 and hyperactivity disorder.

4

5 3.3.2 Adults

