Attachment 3 – Justification for Sample Size Calculations (Supporting information)

- Attachment 3a Child Sample Size Calculations
- Attachment 3b Adult Sample Size Calculations

Sample size calculations were conducted using OpenEpi Version 3.03 (Dean AG, Sullivan KM, Soe MM. OpenEpi: Open Source Epidemiologic Statistics for Public Health, www.OpenEpi.com, updated 2014/09/22). For some health-related endpoints, calculations could not be conducted because of a lack of information in the studies on the parameters needed to make the calculations.

Sample size calculation for mean difference:

$$n_{1} = \frac{(\sigma_{1}^{2} + \sigma_{2}^{2} / \kappa)(z_{1-\alpha/2} + z_{1-\beta})^{2}}{\Delta^{2}}$$
$$n_{2} = \frac{(\kappa * \sigma_{1}^{2} + \sigma_{2}^{2})(z_{1-\alpha/2} + z_{1-\beta})^{2}}{\Delta^{2}}$$

The notation for the formulae are:

$$n_1 = \text{sample size of Group 1}$$

 $n_2 = \text{sample size of Group 2}$
 $\sigma_1 = \text{standard deviation of Group 1}$
 $\sigma_2 = \text{standard deviation of Group 2}$
 $\Delta = \text{ difference in group means}$
 $\kappa = \text{ratio} = n_2/n_1$
 $Z_{1-\alpha/2} = \text{two-sided Z value (eg. Z=1.96 for 95\% confidence interval).}$
 $Z_{1-\beta} = \text{power}$

Where N_2/N_1 is the ratio of the two sample sizes. Then N_2 is simply this ratio multiplied by N_1 . For a type 1 error (or α error) of .05, the $Z_{1-\alpha/2}$ value is 1.96. This calculation is for a two-tailed hypothesis test and equivalent to using a 95% confidence interval to determine statistical significance. For a one-tail test with α =.05, the $Z_{1-\alpha/2}$ in the above equation is replaced by $Z_{1-\alpha}$ and its value is 1.65, equivalent to using a 90% confidence interval to determine statistical significance. For 80% confidence interval to determine statistical significance. The $Z_{1-\beta}$ in the above equation is the Z value for the selected power. For 80% power, $Z_{1-\beta} = 0.84$, for 90% power, $Z_{1-\beta} = 1.28$, and for 95% power, $Z_{1-\beta} = 1.65$. (See Rosner B. Fundamentals of Biostatistics, 7th Edition, equation 8.27, p. 302).

Fleiss JL. Statistical Methods for Rates and Proportions. John Wiley & Sons, 1981.

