Attachment 3a. Sample Size for Child Study

The following notes provide comments and information on the parameters (e.g., standard deviation, disease prevalence) used in the sample size calculations provided in Table 1 for the children study.

Sample size calculations were conducted with type 1 (" α error") set at .05 and type 2 error (" β error) set at .20. Sample sizes per stratum group were calculated. It was considered important that a study have a total sample size so that exposures could be categorized into tertiles (i.e., reference level, medium level, and high level) or quartiles (i.e., reference level, low, medium and high).

Studies were selected that were considered the most representative of U.S. populations exposed via drinking water to PFOA, PFOS and/or PFHxS as a result of the migration of these PFAS chemicals into ground water or surface water sources from the use of aqueous film forming foam (AFFF). The PFOS, PFOA and PFHxS results in the NHANES studies were used in many of the sample size calculations. For those outcomes not included in NHANES studies, the C8 studies were used. Where applicable studies from Taiwan or other major industrialized countries were also used.

Examples:

Lipids

In the C8 study (Frisbee 2010), the mean total cholesterol level in the study population was 160.7 mg/dL and the standard deviation (SD) was 29.3. The sample size calculations assumed the same SD in children exposed and the unexposed group. For hypercholesterolemia (total cholesterol \geq 170 mg/dL), the prevalence in the C8 study was 34.2%.

Uric Acid

In the NHANES study (Geiger 2013), the mean uric acid level in the study population was 5.07 mg/dL with a SD of 1.19. The sample size calculations assumed the same SD in the exposed children and the unexposed group. The prevalence of hyperuricemia (uric acid \geq 6 mg/dL) in the NHANES study was 16%.

Kidney Function

The mean estimated glomerular filtration rate (eGFR) in the C8 study of children and adolescents (Watkins 2013) was 133 mL/min/1.73 m² with a SD of 23.9. The sample size calculations assumed the same SD in the exposes children and the unexposed group.

Attention Deficit/Hyperactivity Disorder (ADHD)

In the C8 study (Stein 2011), the prevalence of participant-reported ADHD was 12.4% and the prevalence for participant-reported + used medications for ADHD was 5.1%. Sample size calculations used the 12.4% prevalence.

Hypersensitivity-related Outcomes

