From an NHANES study (Stein 2016), the prevalence of current asthma and rhinitis among those aged 12-19 were 10.9% and 25.6%, respectively. For atopic dermatitis, the prevalence for children and adolescents (ages 5-17) is about 12% based on data from the National Health Interview Survey.

Sex hormones and Insulin-like growth factor – 1 (IGF-1)

C8 study of children (Lopez-Espinosa 2016)

a. Testosterone

For PFOS, there was a -6.6% difference in the natural log testosterone among girls (per interquartile range of the natural log of PFOS). Among girls, the median testosterone level was 15 ng/dL with an IQR of <LOD, 21 and the LOD of 10 ng/dL. For the sample size calculation of mean difference, the standard deviation was assumed to be equal for the exposed and unexposed groups and equal to 11.85. (Assuming LOD/2 was the lower limit of the IQR, the range = 21 - 5 = 16. Assuming a normal distribution, dividing 16 by 1.35 converts the IQR to a standard deviation, which equaled 11.85)¹. To obtain the mean difference, the median testosterone level (15 ng/dL) was assumed to be the reference level (i.e., the level among the unexposed). The natural log of the median equals 2.71. A 6.6% decrease equals 2.53. Exponentiating 2.53 equals 12.55. The mean difference is then 15 - 12.55 = 2.45.

Assuming a 95% CI and 80% power, the sample size = 368/group; for a ratio of 2, the sample sizes = 552 and 276.

b. IGF-1

For PFHxS, there was a -2.5% difference in the natural log IGF-1 among boys (per interquartile range of the natural log of PFHxS). Among boys, the median IGF-1 level was 147 ng/mL with an IQR of 116, 187. For the sample size calculation of mean difference, the standard deviation was assumed to be equal for the exposed and unexposed groups and equal to 52.6. (The IQR range was 187 - 116 = 71. Assuming a normal distribution, dividing 71 by 1.35 converts the IQR to a standard deviation, which equaled 52.6)¹. To obtain the mean difference, the median IGF-1 level (147 ng/mL) was assumed to be the reference level (i.e., the level among the unexposed). The natural log of the median equals 4.99. A 2.5% decrease equals 4.865. Exponentiating 4.865 equals 129.7. The mean difference is then 147 - 129.7 = 17.3.

Assuming a 95% CI and 80% power, the sample size = 146/group; for a ratio of 2, the sample sizes = 218 and 109.

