For PFOS, there was a -5.9% difference in the natural log IGF-1 among boys (per interquartile range of the natural log of PFOS). This would require considerably smaller sample sizes for IGF-1 than those for PFHxS.

Thyroid function – Children/Adolescents

Taiwan study of children. (Lin 2013)

a. For males aged 12-19, there was a mean difference in the log TSH of -.50 mIU/L for PFOA levels in the 90th percentile (>9.71 ng/ml) compared to the reference level of PFOA exposure. The standard error for the reference group was 0.26 with N=32 in this group; and the standard error for the 90th percentile group was 0.33

with N=6. The standard deviations for the reference and 90th percentile groups were therefore 1.47 and 0.81, respectively.

Assuming a 95% CI and 80% power, the sample size = 89/group; for a ratio of 2, the sample sizes = 158 and 79.

b. For females aged 12-19, there was a mean difference in the log TSH of -.35 mIU/L for PFOA levels in the 90th percentile (>9.71 ng/ml) compared to the reference level of PFOA exposure. The standard error for the reference group was 0.18 with N=71 and the standard error for the 90th percentile group was 0.24 with N=14. The standard deviations for the reference and 90th percentile groups were therefore 1.52 and 0.90, respectively.

Assuming a 95% CI and 80% power, the sample size = 200/group; for a ratio of 2, the sample sizes = 348 and 174.

Additional notes:

Sample sizes for the categorical outcomes in Table 1 were based on the following prevalence in children (also listed in Appendix C Table 1):

Hypercholesterolemia: 34.2% Hyperuricemia: 16% Thyroid disease: 0.6% ADHD 12.4% reported only; 5.1% reported with additional reporting on medications used for ADHD Asthma: 11% Rhinitis: 25.6% Atopic dermatitis: 10.7% Hypertension: 23.4% Obesity: 17%

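### Table 1's asthma size of 2,400 per stratum does not follow from its printed inputs, which give about 4,500

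*Protocol*

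**What the plan says.** Section 3.3.1, Table 1, sizes asthma from an NHANES study of adolescents. The row gives OR 1.2, "Prevalence = 11" per cent and 2,400 per stratum, under a column header of alpha .05 and beta .20. It names a mean PFOA serum level but does not say which exposure groups the odds ratio compares.

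Attachment 3a says of its source that "the prevalence of current asthma and rhinitis among those aged 12-19 were 10.9% and 25.6%, respectively". Its closing list of the prevalences behind Table 1's categorical outcomes reads "Asthma: 11% Rhinitis: 25.6" per cent. Table 1 has no rhinitis row, and no odds ratio for rhinitis appears anywhere.

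On the error rates, Attachment 3a has alpha "set at .05 and type 2 error" at .20. Attachment 3 says of its mean-difference formula: "This calculation is for a two-tailed hypothesis test". Section 3.3.1 wants exposure split into tertiles or "preferably into quartiles".

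The text of Section 3.3.1 says that for several outcomes, including delayed "puberty, and asthma, a total sample sizes of 2,000 children may be sufficient", and adds at once that larger samples would be better. Its summary of outcomes for which 2,000 is enough ends "IQ) and ADHD, rhinitis, and obesity". Asthma is not in that summary.

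**The concern.** The asthma row has the lowest odds ratio among the sized child outcomes and a prevalence close to that of ADHD. ADHD at 12.4% and OR 1.5 is printed as 764 per stratum. Moving from OR 1.5 to OR 1.2 at a slightly lower prevalence should raise the requirement far more than threefold, because the size varies roughly with the inverse square of the difference in proportions.

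Two things are at stake. A stated sample size may be wrong by nearly a factor of two. A sentence in the body text also tells readers that 2,000 children may be enough for an outcome whose own table row, right or wrong, says otherwise.

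**Working it through.** **Inputs.** Reference prevalence p0 = 0.11 and OR = 1.2 (Table 1, asthma row); alpha .05 and power 80% (Table 1 header, Attachment 3a); two-sided (Attachment 3); equal strata; no dropout allowance in the per-stratum figures.

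**Formula.** Exposed proportion: p1 = OR·p0 / (1 − p0 + OR·p0). Size per stratum, with p̄ the mean of p0 and p1:

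n = [1.960·√(2p̄(1−p̄)) + 0.8416·√(p0(1−p0) + p1(1−p1))]² / (p1 − p0)²

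**Does this reproduce other rows?** Attachment 3 prints a formula only for mean differences, so the method for odds-ratio rows has to be checked against the tables:

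- Child high cholesterol (34.2%, OR 1.6): 298; printed 300.
- Child hyperuricemia (16%, OR 1.65): 399; printed 400.
- ADHD (12.4%, OR 1.5): 762; printed 764.
- Elevated ALT in adults (11.2%, OR 1.54 and 1.25): 724 and 2,915; printed 725 and 2,917.

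Not every row agrees this closely. Among those checked, one of the larger gaps is elevated ALT at OR 1.37 (1,418 against 1,570 printed, about 11%). None is near a factor of two.

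**Asthma row.**

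- p1 = 0.132 / 1.022 = 0.12916; p1 − p0 = 0.01916; p̄ = 0.11958.
- Numerator: (1.960 × 0.45887 + 0.8416 × 0.45867)² = (0.8994 + 0.3860)² = 1.6522.
- n = 1.6522 / 0.00036705 = about 4,501 per stratum.

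Variants: 4,537 at 10.9%; 4,605 with continuity correction; 4,503 by the Kelsey formula; 3,546 one-sided; 3,449 if 1.2 is read as a risk ratio. Rounding of the odds ratio does not explain the gap: 1.249 still gives 2,983. The ratio to the printed figure is 4,501 / 2,400 = 1.88.

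**What does come close to 2,400?**

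- OR 1.2 at the rhinitis prevalence of 25.6%: 2,377.
- OR 1.28 at 11%: 2,398.

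**Power at 11% and OR 1.2**, from Φ{[0.01916·√n − 0.8994] / 0.45867}:

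- n = 2,400 (as printed): Φ(0.085) = 53%.
- n = 500 (2,000 / 4, quartiles): Φ(−1.027) = 15%.
- n = 667 (2,000 / 3, tertiles): Φ(−0.882) = 19%.

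The odds ratio detectable with 80% power at 500 versus 500 is about 1.68.

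**Totals implied.** At 2,400 per stratum: 9,600 in quartiles, 7,200 in tertiles. At 4,500: 18,000 and 13,500. The plan has 2,000.

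**The case against.** The strongest reply is that the wrong number changes no design decision. Even 2,400 per stratum is far beyond 2,000 children, so the table as printed already puts asthma out of reach. The sentence in Section 3.3.1 is hedged, cites published studies rather than Table 1, and asthma is left out of the summary of adequately sized outcomes. Section 3.3.2 asks that the sizes be read with caution, Section 1.1.3 says endpoints were not chosen on power, and Section 3.10 bases interpretation on effect size, intervals and consistency. All of this stands and limits the consequence. It does not make the row follow from its inputs. The caution concerns a thin literature, not arithmetic.

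Three stronger readings are tempting.

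- A reader might infer that the rhinitis prevalence was used by mistake. The closeness of 2,377 is suggestive, but it borrows asthma's odds ratio for rhinitis, and a misprinted odds ratio of 1.28 fits equally well. The protocol does not say.
- A reader might infer that the study has 15% power for asthma, full stop. That figure is for a highest-versus-lowest quartile contrast, which the asthma row does not state. Section 3.10 also plans logistic regression on continuous exposure. If, purely as an assumption, 1.2 were the odds ratio per standard deviation of log exposure, the usual approximation gives √(2,000 × 0.11 × 0.89 × (ln 1.2)²) = 2.55, and Φ(2.55 − 1.96) = about 72%.
- A reader might infer that rhinitis should leave the summary list. With no odds ratio or size for it, any power figure would be an assumption, and Table 1 covers only selected outcomes.

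**Conclusion.** The asthma entry in Table 1 is wrong as printed. Its own inputs give about 4,500 per stratum, 1.9 times the stated 2,400, and at those inputs 2,400 would have about 53% power rather than 80%. This rests on a two-sided test with equal strata and 11% as the reference-group prevalence, the convention that reproduces the high-cholesterol, hyperuricemia, ADHD and two of the ALT entries. The cause is open, so the odds ratio, the prevalence or the size could be the item that needs changing.

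The statement that 2,000 children may be enough for asthma is unsupported by either size, even with its caveat. For category contrasts at OR 1.2 the power is about 15% (quartiles) or 19% (tertiles). Nothing here shows that the total of 2,000 is wrong, that the continuous-exposure models have the same low power, or that the rhinitis statement is false.

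**What to change.** 1. Reconcile the odds ratio, prevalence and size in Table 1's asthma row against the source calculation. If OR 1.2 and 11% stand, print about 4,500 per stratum.
2. In Section 3.3.1, take asthma out of the sentence saying that 2,000 may be enough. State instead that, for a highest-versus-lowest contrast at OR 1.2 and 11% prevalence, 2,000 children give about 15% power in quartiles (500 versus 500) or 19% in tertiles (667 versus 667), that the detectable odds ratio in quartiles is about 1.7, and that power for the continuous-exposure models may differ. Recompute these figures if step 1 changes an input.

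The cost is one table row and a sentence or two. No participants, measurements or design features change. The stated position for asthma becomes less favourable.

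### The IGF-1 and testosterone sample sizes take the cited percent change off the logarithm of the median instead of off the median, which inflates the differences 4.7-fold (IGF-1, PFHxS) and 2.5-fold (girls' testosterone) and understates the numbers needed

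*Protocol*

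**What the plan says.** Attachment 3a (sex hormones and IGF-1) takes effects from a cited study of children, expressed per interquartile range (IQR) of ln PFAS. For boys' IGF-1 and PFHxS the effect is -2.5%, the median 147 ng/mL and the quartiles 116 and 187. The conversion reads "The natural log of the median equals 4.99. A 2.5% decrease equals 4.865"; exponentiating gives 129.7 and a difference of 17.3. The result is "Assuming a 95% CI and 80% power, the sample size = 146/group".

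For girls' testosterone and PFOS the effect is -6.6% and the median 15 ng/dL: "A 6.6% decrease equals 2.53. Exponentiating 2.53 equals 12.55". The difference is 2.45, giving 368 per group.

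Table 1 carries these figures as percent changes converted to mean differences with the median as reference, for example "Boys: -2.5% (diff=17.3". It adds boys' testosterone (-5.8%, difference 1.9, 404 per stratum). The total thyroxine row of the same table reads "2.3% change (mean difference = 0.17".

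Section 3.3.1 rests its adequacy statement for 2,000 children partly on "testosterone (about 400 per stratum) and insulin growth factor-1 (IGF-1; 146 per stratum", and its closing summary again names both outcomes as ones that 2,000 or more children can evaluate.

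**The concern.** A percent change from a model of a log outcome applies to the outcome itself. On the log scale it is a constant to be added, not a fraction of the log. A fraction of a logarithm depends on the units. In µg/mL the IGF-1 median is 0.147, and 0.147^0.975 = 0.154, so the protocol's step would turn a 2.5% decrease into an increase.

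The sample sizes vary with the inverse square of the difference, so the error carries through strongly. At stake is whether Section 3.3.1 may describe these outcomes as adequately covered. If it may not, a null result for them could later be read as informative when it is not.

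**Working it through.** **Inputs.** Attachment 3 gives the two-mean formula; on sidedness it says "This calculation is for a two-tailed hypothesis test and equivalent to using a 95% confidence interval to determine statistical significance". With alpha 0.05 and 80% power, (z_0.975 + z_0.80)² = 7.849, and for equal groups n = 2 × SD² × 7.849 / Δ². The SDs are the protocol's: IGF-1 52.6 (71/1.35), girls' testosterone 11.85 (16/1.35), boys' testosterone 9.63.

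**Reproducing the plan.**
- IGF-1: 2 × 52.6² × 7.849 / 17.3² = 145.1, so 146.
- Girls' testosterone: 2 × 11.85² × 7.849 / 2.45² = 367.2, so 368.
- Boys' testosterone: 2 × 9.63² × 7.849 / 1.9² = 403.3, so 404.

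The formula was applied correctly. Only the differences fed into it are wrong.

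**Size of the inflation.**
- IGF-1: 17.3/147 = 11.8%. The cited 2.5% of 147 is 3.675, and 17.3/3.675 = 4.7.
- Girls' testosterone: 2.45/15 = 16.3%. The cited 6.6% of 15 is 0.99, and 2.45/0.99 = 2.5.

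**Conflict with the rest of the document.**
- Thyroxine (Table 1): 0.17/0.023 = 7.39, so the percentage was taken on the raw scale. The IGF-1 method would have given 7.39 - 7.39^0.977 = 0.33 and about 279 per group. Table 1 states 1,080, and the formula with Δ = 0.17 and SD 1.4 gives 1,065.
- ALT and TSH (Attachment 3b): the coefficient is added to the log (3.26 + 0.058; 0.77 + 0.35).

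**Corrected sizes per group, protocol SDs.**

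| Outcome | Δ | n, raw scale | n, ln scale | Protocol |
|---|---|---|---|---|
| IGF-1, PFHxS | 0.025 × 147 = 3.675 | 3,216 | 3,060–3,140 | 146 |
| Testosterone, girls | 0.066 × 15 = 0.99 | 2,250 | about 3,800 | 368 |
| Testosterone, boys | 0.058 × 13.54 = 0.786 | about 2,360 | – | 404 |
| IGF-1, PFOS | 0.059 × 147 = 8.673 | 578 | – | none stated |

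The ln-scale SDs are ln(187/116)/1.35 = 0.354 and ln(21/5)/1.35 = 1.063; the second uses the protocol's LOD/2 = 5 as lower quartile. The IGF-1 range comes from Δ = -ln(0.975) = 0.0253 or Δ = 0.025. The boys' median is not in the document; 13.54 is back-solved from m - m^0.942 = 1.9 and is an assumption.

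**Power at the planned size.** 2,000 children give 500 per quartile, 250 per quartile within one sex, or 667 per tertile.

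| Effect (per IQR) | 250 | 500 | 667 |
|---|---|---|---|
| IGF-1, PFHxS | 12% | 20% | 25% |
| Testosterone, girls | 15% | 26% | 33% |
| IGF-1, PFOS | 45% | 74% | 85% |

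**The case against.** The best defence of the step is its wording: Attachment 3a speaks of a percent difference in the natural log of the hormone. Read literally, that would license it. It does not stand, because such a quantity depends on the units and Table 1 labels the same figures as percent changes relative to the median. The cited study cannot be checked here. Reading the figures as log coefficients instead gives 3,298 and 2,402 per group, so the conclusion is the same.

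Three other objections do stand in part.

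- **The chemical matters.** A reader might infer that IGF-1 is far from detectable at every cited effect and should be dropped from Section 3.3.1. The document does not support that: Attachment 3a also cites -5.9% for PFOS in boys, which needs about 578 per group. Its remark that PFOS needs considerably fewer than PFHxS keeps its ordering, although 578 exceeds the printed 146.
- **The contrast matters.** The effects are per IQR of ln PFAS, while the strata are quartiles. If ln PFAS is roughly normal (assumption), the mean difference between quartiles 4 and 1 is about 1.88 IQRs. The sizes then fall by 1.88² = 3.55, to about 905 (IGF-1, PFHxS) and 633 (girls' testosterone). Both still exceed 500.
- **The analysis matters.** Section 3.10 also plans continuous exposure models. Under the same assumption, 1,000 children of one sex give power of about 37% (IGF-1, PFHxS), 50% (girls' testosterone) and 97% (IGF-1, PFOS).

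The protocol also says that endpoints were not chosen on power, that sample-size estimates need caution, and that IQR/1.35 can understate the SD. These are fair limits on how much the numbers decide, but they do not cover a wrong conversion.

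**Conclusion.** The point holds for the conversion and for the adequacy statements built on it. The figures of 146, 368 and 404 follow only from inflated differences. At the effects cited, IGF-1 for PFHxS needs about 3,200 per group and girls' testosterone about 2,250, more on the ln scale. Both remain short at 500 per stratum under the more favourable quartile contrast.

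These sizes keep the protocol's SDs, alpha, power and per-IQR effects, so they correct the protocol's own calculation and are not definitive requirements for the study. The boys' figure depends on a back-solved median. IGF-1 for PFOS is better placed: about 74% power at 500 per quartile and 85% at 667 per tertile, but 45% at 250 boys per quartile.

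A reader might go on to infer that 2,000 children is the wrong total. Nothing in the document shows that these rows determined it, and Section 3.3.1 already keeps outcomes it regards as only possibly covered, such as thyroid function.

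**What to change.** In Attachment 3a and Table 1, use difference = median × percent/100, or work wholly on the ln scale, and say which. Restate per group:

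- IGF-1 for PFHxS: about 3,200 (ln scale about 3,060–3,140).
- Girls' testosterone: about 2,250 (ln scale about 3,800 with LOD/2 as lower quartile).
- Boys' testosterone: recomputed from the source median, which should be printed.
- IGF-1 for PFOS: a separate entry, about 578.

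In Section 3.3.1, delete the two per-stratum figures for testosterone and IGF-1. Remove testosterone and IGF-1 for PFHxS from the outcomes called sufficiently covered, in both the main paragraph and the summary, and qualify IGF-1 by chemical with the power shown above. Add a sentence that the effects are per IQR of ln PFAS and that a quartile 4 versus quartile 1 contrast would need fewer children.

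The cost is a recalculation of the testosterone and IGF-1 rows of Table 1, edits to one attachment and a few sentences. Recruitment, measurements and design are unaffected.
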